10.3.1 Definition of AE

AE definition

- An AE is any untoward medical occurrence in a clinical study participant, temporally associated with the use of study intervention, whether or not considered related to the study intervention.
- Note: An AE can therefore be any unfavorable and unintended sign (including an abnormal laboratory finding), symptom, or disease (new or exacerbated) temporally associated with the use of a study intervention.
- Note: For purposes of AE definition, study intervention (also referred to as Sponsor's product) includes any pharmaceutical product, biological product, vaccine, diagnostic agent, medical device, combination product, or protocol specified procedure whether investigational or marketed (including placebo, active comparator product, or run-in intervention), manufactured by, licensed by, provided by, or distributed by the Sponsor for human use in this study.

Events meeting the AE definition

- Any abnormal laboratory test results (hematology, clinical chemistry, or urinalysis) or other safety assessments (eg, ECG, radiological scans, vital signs measurements), including those that worsen from baseline, considered clinically significant in the medical and scientific judgment of the investigator.
- Exacerbation of a chronic or intermittent preexisting condition including either an increase in frequency and/or intensity of the condition.
- New conditions detected or diagnosed after study intervention administration even though it may have been present before the start of the study.
- Signs, symptoms, or the clinical sequelae of a suspected drug-drug interaction.
- Signs, symptoms, or the clinical sequelae of a suspected overdose of either study intervention or a concomitant medication.
- For all reports of overdose (whether accidental or intentional) with an associated AE, the AE term should reflect the clinical symptoms or abnormal test result. An overdose without any associated clinical symptoms or abnormal laboratory results is reported using the terminology "accidental or intentional overdose without adverse effect."
- Any new cancer or progression of existing cancer.

Events NOT meeting the AE definition

- Medical or surgical procedure (eg, endoscopy, appendectomy): the condition that leads to the procedure is the AE.
- Situations in which an untoward medical occurrence did not occur (social and/or convenience admission to a hospital).
- Anticipated day-to-day fluctuations of preexisting disease(s) or condition(s) present or detected at the start of the study that do not worsen.
- Surgical procedure(s) planned prior to informed consent to treat a preexisting condition that has not worsened.
- Refer to Section 8.4.6 for protocol-specific exceptions.

10.3.2 Definition of SAE

If an event is not an AE per definition above, then it cannot be an SAE even if serious conditions are met.

An SAE is defined as any untoward medical occurrence that, at any dose:

a. Results in death

b. Is life-threatening

• The term "life-threatening" in the definition of "serious" refers to an event in which the participant was at risk of death at the time of the event. It does not refer to an event, which hypothetically might have caused death, if it were more severe.

c. Requires inpatient hospitalization or prolongation of existing hospitalization

• Hospitalization is defined as an inpatient admission, regardless of length of stay, even if the hospitalization is a precautionary measure for continued observation. (Note: Hospitalization for an elective procedure to treat a preexisting condition that has not worsened is not an SAE.) A preexisting condition is a clinical condition that is diagnosed prior to the use of an MSD product and is documented in the participant's medical history.

d. Results in persistent or significant disability/incapacity

• The term disability means a substantial disruption of a person's ability to conduct normal life functions.

• This definition is not intended to include experiences of relatively minor medical significance such as uncomplicated headache, nausea, vomiting, diarrhea, influenza, and accidental trauma (eg, sprained ankle) that may interfere with or prevent everyday life functions but do not constitute a substantial disruption.

e. Is a congenital anomaly/birth defect

• In offspring of participant taking the product regardless of time to diagnosis.

f. Other important medical events

- Medical or scientific judgment should be exercised in deciding whether SAE reporting is appropriate in other situations such as important medical events that may not be immediately life-threatening or result in death or hospitalization but may jeopardize the participant or may require medical or surgical intervention to prevent 1 of the other outcomes listed in the above definition. These events should usually be considered serious.
- Examples of such events include invasive or malignant cancers, intensive treatment in an emergency room or at home for allergic bronchospasm, blood dyscrasias or convulsions that do not result in hospitalization, or development of drug dependency or drug abuse.

10.3.3 Additional Events Reported

Additional events that require reporting

In addition to the above criteria, AEs meeting either of the below criteria, although not serious per ICH definition, are reportable to the Sponsor.

- Is a cancer
- Is associated with an overdose

10.3.4 Recording AE and SAE

AE and SAE recording

- When an AE/SAE occurs, it is the responsibility of the investigator to review all documentation (eg, hospital progress notes, laboratory, and diagnostics reports) related to the event.
- The investigator will record all relevant AE/SAE information on the AE CRFs/worksheets at each examination.
- It is not acceptable for the investigator to send photocopies of the participant's medical records to the Sponsor in lieu of completion of the AE CRF page.

- There may be instances when copies of medical records for certain cases are requested by the Sponsor. In this case, all participant identifiers, with the exception of the participant number, will be blinded on the copies of the medical records before submission to the Sponsor.
- The investigator will attempt to establish a diagnosis of the event based on signs, symptoms, and/or other clinical information. In such cases, the diagnosis (not the individual signs/symptoms) will be documented as the AE/SAE.

Assessment of intensity/toxicity

- An event is defined as "serious" when it meets at least 1 of the predefined outcomes as described in the definition of an SAE, not when it is rated as severe.
- The investigator will make an assessment of intensity for each AE and SAE (and other reportable safety event) by recording the grade according to the NIH DAIDS Table for Grading the Severity of Adult and Pediatric Adverse Events, version 2.1. Any AE which changes DAIDS grade over the course of a given episode will have each change of grade recorded on the AE CRFs/worksheets.
 - Grade 1 Mild event: Mild symptoms causing no or minimal interference with usual social and functional activities with intervention not indicated.
 - Grade 2 Moderate event: Moderate symptoms causing greater than minimal interference with usual social and functional activities with intervention indicated.
 - Grade 3 Severe event: Severe symptoms causing inability to perform usual social and functional activities with intervention or hospitalization indicated.
 - Grade 4 Potentially life-threatening event: Potentially life-threatening symptoms causing inability to perform basic self-care functions with intervention indicated to prevent permanent impairment, persistent disability, or death.
 - Grade 5 Death: Deaths related to an AE.

Assessment of causality

- Did the Sponsor's product cause the AE?
- The determination of the likelihood that the Sponsor's product caused the AE will be provided by an investigator who is a qualified physician. The investigator's signed/dated initials on the source document or worksheet that supports the causality noted on the AE form, ensures that a medically qualified assessment of causality was done. This initialed document must be retained for the required regulatory time frame. The criteria below are intended as reference guidelines to assist the investigator in assessing the likelihood of a relationship between the test product and the AE based upon the available information.

- The following components are to be used to assess the relationship between the Sponsor's product and the AE; the greater the correlation with the components and their respective elements (in number and/or intensity), the more likely the Sponsor's product caused the AE:
 - **Exposure:** Is there evidence that the participant was actually exposed to the Sponsor's product such as: reliable history, acceptable compliance assessment (pill count, diary, etc), expected pharmacologic effect, or measurement of drug/metabolite in bodily specimen?
 - **Time Course:** Did the AE follow in a reasonable temporal sequence from administration of the Sponsor's product? Is the time of onset of the AE compatible with a drug-induced effect (applies to studies with investigational medicinal product)?
 - Likely Cause: Is the AE not reasonably explained by another etiology such as underlying disease, other drug(s)/vaccine(s), or other host or environmental factors.
 - **Dechallenge:** Was the Sponsor's product discontinued or dose/exposure/frequency reduced?
 - If yes, did the AE resolve or improve?
 - If yes, this is a positive dechallenge.
 - If no, this is a negative dechallenge.

(Note: This criterion is not applicable if: (1) the AE resulted in death or permanent disability; (2) the AE resolved/improved despite continuation of the Sponsor's product; (3) the study is a single-dose drug study; or (4) Sponsor's product(s) is/are only used 1 time.)

- Rechallenge: Was the participant re-exposed to the Sponsor's product in this study?
 - If yes, did the AE recur or worsen?
 - If yes, this is a positive rechallenge.
 - If no, this is a negative rechallenge.

(Note: This criterion is not applicable if: (1) the initial AE resulted in death or permanent disability, or (2) the study is a single-dose drug study; or (3) Sponsor's product(s) is/are used only 1 time.)

MK-4482-013-05 FINAL PROTOCOL

16-OCT-2022

NOTE: IF A RECHALLENGE IS PLANNED FOR AN AE THAT WAS SERIOUS AND MAY HAVE BEEN CAUSED BY THE SPONSOR'S PRODUCT, OR IF RE-EXPOSURE TO THE SPONSOR'S PRODUCT POSES ADDITIONAL POTENTIAL SIGNIFICANT RISK TO THE PARTICIPANT THEN THE RECHALLENGE MUST BE APPROVED IN ADVANCE BY THE SPONSOR CLINICAL DIRECTOR, AND IF REQUIRED, THE IRB/IEC.

- **Consistency with study intervention profile:** Is the clinical/pathological presentation of the AE consistent with previous knowledge regarding the Sponsor's product or drug class pharmacology or toxicology?
- The assessment of relationship will be reported on the CRFs/worksheets by an investigator who is a qualified physician according to their best clinical judgment, including consideration of the above elements.
- Use the following scale of criteria as guidance (not all criteria must be present to be indicative of a Sponsor's product relationship).
 - Yes, there is a reasonable possibility of Sponsor's product relationship:
 - There is evidence of exposure to the Sponsor's product. The temporal sequence of the AE onset relative to the administration of the Sponsor's product is reasonable. The AE is more likely explained by the Sponsor's product than by another cause.
 - No, there is not a reasonable possibility of Sponsor's product relationship:
 - Participant did not receive the Sponsor's product OR temporal sequence of the AE onset relative to administration of the Sponsor's product is not reasonable OR the AE is more likely explained by another cause than the Sponsor's product. (Also entered for a participant with overdose without an associated AE.)
- The investigator must review and provide an assessment of causality for each AE/SAE and document this in the medical notes.
- There may be situations in which an SAE has occurred and the investigator has minimal information to include in the initial report to the Sponsor. However, it is very important that the investigator always make an assessment of causality for every event before the initial transmission of the SAE data to the Sponsor.
- The investigator may change their opinion of causality in light of follow-up information and send an SAE follow-up report with the updated causality assessment.
- The causality assessment is 1 of the criteria used when determining regulatory reporting requirements.

Follow-up of AE and SAE

- The investigator is obligated to perform or arrange for the conduct of supplemental measurements and/or evaluations as medically indicated or as requested by Sponsor to elucidate the nature and/or causality of the AE or SAE as fully as possible. This may include additional laboratory tests or investigations, histopathological examinations, or consultation with other healthcare professionals.
- New or updated information will be recorded in the CRF.
- The investigator will submit any updated SAE data to the Sponsor within 24 hours of receipt of the information.

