- MK-4482-006 (EIDD-2801-2003; NCT04405570) was a Phase 2a, randomized, doubleblind, placebo-controlled study to evaluate the safety, tolerability, and efficacy of MOV (Q12H for 5 days) in nonhospitalized adults with COVID-19. The study is complete. A total 204 participants were randomized; of these participants, 140 received at least 1 dose of MOV (23 in the 200 mg BID group, 62 in the 400 mg BID group, and 55 in the 800 mg BID group) and 62 received placebo. Virology data from this study showed a reduction in recovery of infectious virus in MOV-treated participants compared with placebo recipients at Day 5. MOV was generally well tolerated with a comparable incidence of AEs across the intervention groups. The most frequently reported AEs (>2%) in the MOV groups combined were headache (4.3%), ALT increased (2.9%), insomnia (2.9%), dizziness (2.1%), and AST increased (2.1%). The most frequently reported AEs (>2%) in the placebo group were insomnia (6.5%), headache (4.8%), and ALT increased (3.2%). There were no drug-related AEs leading to study intervention discontinuation, no deaths, no drug-related SAEs, and no drug-related Grade 3 or higher AEs.
- Two Phase 2/3 randomized, double-blind, placebo-controlled studies are now clinically complete in hospitalized (MK-4482-001; MOVe-IN) and nonhospitalized (MK-4482-002; MOVe-OUT) adults with COVID-19 to evaluate the efficacy, safety, and PK of MOV (Q12H for 5 days). Enrollment in Part 1 (Phase 2) of each of these studies has been completed, as well as Part 2 (Phase 3) of study MK-4482-002. A summary of interim data from MK-4482-001 and MK-4482-002 that supports dose selection for MK-4482-013 is provided in Section 4.3.1 of this protocol. Summaries of safety data for MK-4482-001 and MK-4482-002 are provided below.

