8.4 Adverse Events, Serious Adverse Events, and Other Reportable Safety Events

The definitions of an AE or SAE, as well as the method of recording, evaluating, and assessing causality of AE and SAE and the procedures for completing and transmitting AE, SAE, and other reportable safety event reports can be found in Appendix 3.

Adverse events, SAEs, and other reportable safety events will be reported by the participant (or, when appropriate, by a caregiver, surrogate, or the participant's legally authorized representative).

The investigator and any designees are responsible for detecting, documenting, and reporting events that meet the definition of an AE or SAE as well as other reportable safety events.

Investigators remain responsible for following up AEs, SAEs, and other reportable safety events for outcome according to Section 8.4.3.

The investigator, who is a qualified physician, will assess events that meet the definition of an AE or SAE as well as other reportable safety events with respect to seriousness, intensity/toxicity and causality.

8.4.1 Time Period and Frequency for Collecting AE, SAE, and Other Reportable Safety Event Information

For participating household contacts, all AEs, SAEs, and other reportable safety events that occur after the participant provides documented informed consent, but before intervention randomization, must be reported by the investigator if the event causes the participant to be excluded from the study, or is the result of a protocol-specified intervention.

From the time of intervention randomization, through 14 days after cessation of study intervention, all AEs, SAEs, and other reportable safety events must be reported by the investigator.

Additionally, any SAE brought to the attention of an investigator at any time outside the period specified in the previous paragraph must be reported immediately to the Sponsor if the event is considered related to study intervention.

For participating index cases, all AEs, SAEs, and other reportable safety events that occur after the participant provides documented informed consent, but before allocation, must be reported by the investigator if the event causes the participant to be excluded from the study, or is the result of a protocol-specified intervention.

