9.1 Statistical Analysis Plan Summary

Key elements of the statistical analysis plan are summarized below; the comprehensive plan is provided in Section 9.2 to Section 9.12.

Study Design Overview	A Phase 3, Multicenter, Randomized, Double-blind, Placebo- controlled Study to Evaluate the Efficacy and Safety of MK-4482 for the Prevention of COVID-19 (Laboratory-confirmed SARS- CoV-2 Infection With Symptoms) in Adults Residing With a Person With COVID-19.		
Treatment Assignment	 Approximately 1376 participants (regardless of SARS-CoV-2 results in baseline NP swabs) will be randomized in a 1:1 ratio (stratified per Section 6.3.2) to receive either MOV or placebo, Q12H for 5 days. MOV 800 mg (n~688) Placebo (n~688) 		
Analysis Populations	Efficacy: mITT Safety: APaT		
Primary Endpoint(s)	Efficacy: Percentage of participants with undetectable SARS-CoV-2 in baseline NP swabs developing COVID-19 through Day 14. Safety: AEs, and AEs leading to discontinuation of study intervention.		
Secondary Endpoints	 Percentage of participants (regardless of SARS-CoV-2 results in baseline NP swabs) developing COVID-19 through Day 14 Percentage of participants with undetectable SARS-CoV-2 in baseline NP swabs developing COVID-19 through Day 29. Percentage of participants with undetectable SARS-CoV-2 in baseline NP swabs having viral transmission through Day 14. Percentage of participants with detectable SARS-CoV-2 in baseline NP swabs having viral transmission through Day 14. Percentage of participants with detectable SARS-CoV-2 in baseline NP swabs developing COVID-19 through Day 14. 		
Statistical Methods for Key Efficacy Analyses			
Statistical Methods for Key Safety Analyses			

x / • • •	
Interim Analyses	One IA will be performed to evaluate safety and futility with respect to the primary efficacy hypothesis. Results will be reviewed by an eDMC. A summary of the IA is provided below. Further details are provided in Section 9.7.
	• Timing: To be conducted when approximately 55% of the participants with undetectable SARS-CoV-2 in baseline NP swabs have either completed the Day 14 visit or discontinued from the study prior to the Day 14 visit.
	• Testing: The primary efficacy hypothesis will be tested.
Multiplicity	A gatekeeping strategy will be used to control the overall FWER associated with the primary and secondary analyses.
	The following efficacy hypotheses will be tested sequentially at a one-sided 2.49% Type I error rate at final analyses:

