9.6.2 Statistical Methods for Safety Analyses

Safety and tolerability will be assessed by clinical review of all relevant parameters including AEs and laboratory tests.

The analysis of safety results for participants will follow a tiered approach (Table 6). The tiers differ with respect to the analyses that will be performed. Adverse events (specific terms as well as system organ class terms) and events that meet PDLCs in laboratory will be classified as belonging to "Tier 2" or "Tier 3" based on the number of events observed.

Safety parameters or adverse events of special interest that are identified a priori constitute "Tier 1" safety endpoints that will be subject to inferential testing for statistical significance. No a priori clinical events of concern have been identified for this study.

Tier 2 parameters will be assessed via point estimates with 95% confidence intervals provided for differences in the percentage of participants with events (via the unstratified Miettinen and Nurminen method (1985) [Miettinen, O. and Nurminen, M. 1985]).

Because many 95% confidence intervals for Tier 2 events may be provided without adjustment for multiplicity, the confidence intervals should be regarded as a helpful descriptive measure to be used in review, not a formal method for assessing the statistical significance of the between-group differences in adverse events and safety parameters that meet predefined limits of change.

ECIs identified in Section 8.4.7 are considered Tier 2 events, as well as the broad AE categories consisting of the percentage of participants with any AE, a drug-related AE, a serious AE, an AE, which is both drug-related and serious, and discontinuation due to an AE will be considered Tier 2 endpoints. In addition, individual AEs observed in $\geq 1\%$ of participants in any intervention group will be categorized as a Tier 2 event. Events reported less frequently than in 1% of participants would obscure the assessment of the overall safety profile and add little to the interpretation of potentially meaningful differences.

Safety endpoints that are not Tier 2 events are considered Tier 3 events. Only point estimates by treatment group are provided for Tier 3 safety parameters.

Continuous Safety Measures

For continuous measures such as changes from baseline in laboratory parameters, summary statistics for baseline, on-treatment, and change from baseline values will be provided by treatment group in Table format.

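### Every AE is graded for severity, but the investigator's grade enters no specified safety analysis, so a shift to severe, non-serious, non-laboratory AEs that neither stop treatment nor change incidence would show in no listed comparison

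*Combined protocol and SAP*

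**What the plan says.** Section 8.4 has the investigator assess each event "with respect to seriousness, intensity/toxicity and causality". Section 10.3.4 repeats the intensity requirement ("The investigator will make an assessment of intensity for each AE and SAE"), names DAIDS version 2.1 as the scale, and asks for each change of grade within an episode to be recorded. The same section keeps severity apart from seriousness: an event is serious because of its outcome, "not when it is rated as severe".

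The SAP summary (Section 9.1) gives the primary safety endpoints as "Safety: AEs, and AEs leading to discontinuation of study intervention". Section 9.6.2 names no Tier 1 events. Its Tier 2 comparisons are ECIs, "the broad AE categories consisting of the percentage of participants with any AE, a drug-related AE, a serious AE", AEs both drug-related and serious, and discontinuation due to an AE. Table 6 adds specific AEs, system organ classes and laboratory limits of change reaching 1% in either arm. For the remainder, "Safety endpoints that are not Tier 2 events are considered Tier 3 events", and Tier 3 gives point estimates by arm only.

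Grade does appear once in the safety analysis. Section 9.4.2 classifies laboratory values by whether they fall outside limits adapted from DAIDS and are worse in grade than at baseline.

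**The concern.** The investigator judges three attributes of every AE. Two of them, seriousness and causality, reach the between-arm comparisons. The third, intensity, does not. The incidence rows count a Grade 1 and a Grade 3 episode of the same symptom alike, and the serious-AE row is by definition not a severity measure.

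Safety and tolerability is a primary objective, and the participants are asymptomatic household contacts taking a drug for prevention. For them, inability to carry out usual activities, which is how Section 10.3.4 describes Grade 3, bears on benefit-risk even when no seriousness criterion is met. A plan followed to the letter could report similar AE incidence, SAEs and discontinuations while the severity of AEs differed between arms. Any severity comparison made after unblinding would then be post hoc.

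**Working it through.** **Step 1. Follow each attribute from collection to analysis.**

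| Attribute (8.4, 10.3.4) | Between-arm 95% CI (9.6.2, Table 6) |
|---|---|
| Seriousness | Yes: serious AE; serious and drug-related AE |
| Causality | Yes: drug-related AE; serious and drug-related AE |
| DAIDS grade of a laboratory value | Yes: limits of change, if incidence is at least 1% in either arm |
| Investigator-assigned grade of an AE | None listed; no Tier 3 summary named |

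**Step 2. Ask what the other rows would catch.**
- A severe event that leads to admission or is life-threatening is an SAE (10.3.2) and appears there.
- A severe event that stops dosing appears under discontinuation due to AE. Dosing lasts 5 days, whereas AEs are collected until 14 days after the last dose (8.4.1), so a severe AE after the last dose cannot register in this row.
- An excess in the number of participants with, say, headache or nausea would be compared in the specific-AE and organ-class rows at 1% or more.
- Laboratory toxicity is covered by the limits of change and the hepatic ECI (8.4.7).
- What remains is a shift to greater severity among AEs that are non-serious, non-laboratory and do not stop treatment, with incidence unchanged.

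**Step 3. The plan's own figure.** This point disputes no stated number. As a check on the sample size, Section 9.9.3 gives a 49.8% chance of seeing at least one AE of 0.1% frequency among 688 participants: 1 − 0.999^688 = 0.498, which reproduces.

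**Step 4. An example of the gap.** Inputs: n = 688 per arm (9.9.3). The event counts are assumed, because the documents give no Grade 3 or higher rate for this population. Suppose 206 participants per arm (29.9%) have any AE, and some AEs that would have been mild become severe on MOV, giving 28 v 14 participants with Grade 3 or higher.
- Any AE, 206 v 206: difference 0, Miettinen-Nurminen 95% CI −4.8 to +4.8 points.
- Grade 3 or higher, 28 v 14: difference 14/688 = 2.0 points. The score statistic at zero difference uses the pooled rate 42/1376 = 0.0305. Its standard error is √(0.0305 × 0.9695 × 2/688 × 1376/1375) = 0.00928, so Z = 0.02035/0.00928 = 2.19. The Miettinen-Nurminen 95% CI is 0.2 to 4.0 points.

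**Step 5. How informative would the new row be?** The interval excludes zero exactly when the score statistic passes ±1.96. The table sums the binomial probabilities, with 688 per arm, of all outcomes where Z > 1.96, that is, more events on MOV.

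| Assumed Grade ≥3 rate, MOV v placebo | Chance the CI shows more events on MOV |
|---|---|
| 1% v 0.5% | 17% |
| 3% v 2% | 22% |
| 2% v 1% | 34% |
| 4% v 2% | 60% |
| 3% v 1% | 78% |
| 5% v 2% | 87% |

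The row would be reasonably sensitive to a difference of 2 points or more and weak for 1 point or less.

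**The case against.** **Grade is not unused.** A reader might infer that no safety analysis uses severity grade. Section 9.4.2 contradicts that. Section 4.2.1.2 singles out bone marrow and liver for monitoring, and both are followed through laboratory values. This stands, and it confines the point to investigator-assigned grades of non-laboratory AEs.

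**Most severe events would still be seen.** A reader might also infer that severe AEs on MOV would go unnoticed. They would not if they hospitalised, threatened life, stopped treatment, or raised the incidence of a term or organ class reaching 1%. This too stands. The short dosing period weakens the discontinuation row less than it may seem: Section 2.2.3.1 gives an effective plasma half-life of about 1 hour and a terminal phase of up to about 19 hours, and Section 4.2 reports no evidence of delayed toxicity, so drug-caused intolerance would be expected mainly while dosing.

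**The rates are assumed.** No document supports any pair in the table. The nearest evidence is the Phase 2a trial in nonhospitalised patients, summarised as having "no drug-related Grade 3 or higher AEs". Zero of 140 MOV recipients gives a two-sided 95% upper limit of 1 − 0.025^(1/140) = 2.6%. That covers drug-related events only, at three doses (55 participants at 800 mg), in patients with COVID-19. It does not settle the rate here, but it is a reason to show the low end of the range. The Phase 2a sentence is also thin precedent for a grade summary, since the larger Phase 2/3 summaries rely mainly on any AE, drug-related AEs, SAEs and deaths.

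**Silence is not proof that grades will never be tabulated.** Section 9.6.2 opens with clinical review of all relevant parameters, and the eDMC charter and supplemental SAP are not among the documents. A claim that nobody will look at grade is therefore unsupported. However, Section 9.6 says it sets out the methods for primary and secondary objectives and leaves exploratory ones to the supplemental SAP, so a tolerability summary for a primary objective belongs in 9.6.2.

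**A Grade 3 or higher row would mix in disease.** COVID-19 and COVID-19 pneumonia were among the frequent AEs in the earlier trials. If MOV prevents them, that could mask poorer tolerability. This stands and is met in the fix.

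**Conclusion.** The point holds in a narrow form. The investigator-assigned AE grade enters no analysis specified in Section 9.6.2 or Table 6, and one pattern of harm would show in no listed comparison: a shift to severe, non-serious, non-laboratory AEs that do not stop treatment and leave incidence unchanged. The finding rests on the text of those sections and not on any rate. The assumed rates bear only on how useful the added row would be: informative for differences of 2 points or more from a low placebo rate, and limited below that. No hypothesis, alpha level or stated figure is affected. This is an inexpensive improvement to the analysis of a primary objective, not an error that undermines the trial.

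**What to change.** In Section 9.6.2 and the Tier 2 block of Table 6, add two rows: *any AE of DAIDS Grade ≥3* and *any drug-related AE of DAIDS Grade ≥3*. Count each participant once by worst grade, in the APaT population, with the same unstratified Miettinen-Nurminen 95% CI as the other broad categories. Show the first row also with COVID-19 disease terms removed, the term list being fixed before unblinding, because those events can reflect efficacy. Add a Tier 3 table of participants by worst grade and arm.

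The grades are already on the AE case report form, so nothing new is collected. The cost is some SAP wording, a few table rows and a few more confidence intervals without multiplicity adjustment, which Section 9.6.2 already treats as descriptive.
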